We propose to test the intervention “INcentives and ReMINDers to Improve Long-term Medication Adherence” (INMIND) in a pilot, parallel group randomized controlled trial (RCT) at the Mildmay Uganda HIV clinic in Kampala, Uganda with two intervention groups and a control group using an even allocation ratio of 1:1:1 between the three study groups. All participants (including in the control group) will receive information about the importance of behavioral routines, as is part of the standard adherence counseling for treatment initiators at Mildmay Uganda and will create personalized ART adherence anchoring strategies. The first intervention group will additionally receive text message reminders of their anchoring strategy, and the second intervention group will receive both the text message reminders and small incentives conditional on taking ART pills within a time window that corresponds to participants’ personalized anchoring strategy. We hypothesize that the text message reminders and incentives will increase participants’ use of their anchoring strategy, and thus medication adherence will be better maintained after the intervention ends in our two intervention groups relative to the control group. We also expect to see stronger maintenance in the intervention group receiving both reminder messages and incentives than the intervention group receiving only reminder messages.

Methods

Ethics Approval

This pilot RCT has been funded by the National Institutes of Mental Health in the United States (R34MH122331) and approved by the RAND Human’s Subjects Protection Committee (2020-N0632), Mildmay Uganda Research Ethics Committee (MUREC) (0701-2021), as well as the Uganda National Council for Science and Technology (HS128ES). As of February 18, 2022, recruitment was completed.

Study Design

This study will use a three-armed randomized controlled trial (two intervention groups and one control group) with randomization at the individual level. The interventions will be administered for a period of three months from the baseline survey. During the intervention period, MEMS data readings will be collected monthly, wherein prize drawings for eligible participants in the Incentives group will be carried out. Since the population of interest are treatment initiators, the monthly study visits are expected to coincide with the monthly clinic visits as mandated for

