Additionally, clients who are not mentally fit to understand the consenting or study procedures, as well as clients who speak neither English nor Luganda (the local language spoken by the majority of people in and around Kampala) were excluded. As both intervention groups rely on the receipt of text messages, clients who don't own a cell phone or have access to one will also be excluded.

Participation in another adherence study as well as non-ability or non-desire to use MEMS caps regularly throughout the course of the study will also be a basis for exclusion. Consequently, if the baseline MEMS reading suggests that participants opened their pill bottle less than 30% of days, and if that was not a consequence of low adherence, then the participant will be given a transport refund and will be unenrolled from the study. Finally, clients coming outside regular clinic working hours will be excluded.

Randomization and Allocation

Participants will be randomly assigned to either one of the treatment arms (T1 = *Messages*; T2 = *Incentives*) or the control arm after consenting but will only be informed of their assignment after the baseline survey is over to minimize any potential influence of the assignment on the baseline survey responses. The distribution ratios for the randomization will be 1:1:1 and the assignment will be carried out through a computer-generated randomization component built into the baseline survey administration software, called Questionnaire Development System. The random assignment (to either the control group or one of the two intervention arms) will be revealed at the end of the baseline survey to both the participant and the study coordinator, who will therefore not know the respondent's treatment assignment during the survey. Given the

nature of the intervention, neither the interviewers nor the participants can be blinded to the treatment status. However, the data analyst who will conduct the impact analysis will be blinded to treatment assignment.

Procedures

Interventions

The pilot will include a control arm, along with two intervention arms – *Messages* (T1) and *Incentives* (T2).

Control Group: Usual Care

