The fourth outcome will be calculated using the same procedures as *Outcome 3*. However, the data from which the measure will be assessed will be collected during the post-intervention period.

The team will also assess two secondary efficacy measures, as described below:

Secondary Outcome 1: Retention in care

Retention in care is an important metric of treatment adherence. Failure to remain in care is a commonly observed problem for treatment initiators. To assess how well participants will continue to remain in care, Mildmay electronic records will be used to evaluate the number of study participants who fail to observe their regularly scheduled clinic visits. Participants who don't make any clinic visits for six months or more will be considered lost to follow up. The study coordinator will call them using the tracking information collected for the study to inquire about their reason for stopping care at the Mildmay clinic. This outcome will be measured as an indicator of whether the participants are still active clients at the clinic at the end of the nine-month study.

Secondary Outcome 2: Viral Suppression

HIV RNA (viral load) is our final outcome measure. According to the AIDS Clinical Trials Group, virological failure is defined as a confirmed viral load > 200 copies/mL. Below this level, the viral load is considered undetectable. Importantly, this is a reliable biological measure of ART adherence, since strong adherence leads to lower viral load. Given the intervention design, viral load will be an important complementary measure of adherence. The analysis will examine the intervention effects on the likelihood of being virally suppressed at the end of the nine-month study period.

Data Analysis

[Statistical Methods and Analyses](#)

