Feasibility and acceptability will be analyzed using summary statistics derived directly from our self-reported measures. To estimate preliminary efficacy, statistical analyses comparing group-level differences in the secondary and tertiary outcome measures will be performed. An Analysis of Covariance framework will be used to test for group differences in each secondary and tertiary outcome, controlling for the participant characteristics that are found to differentiate the groups at baseline. For analyses of dichotomous variables, such as viral suppression, a non-parametric McNemar's test and an analogous multiple logistic regression will be used to control for covariates to assess group differences. In addition to static comparisons of group means for each outcome at three-month intervals, the longitudinal nature of the data will be leveraged by using repeated measures and time-series techniques. Specifically, a linear mixed model with repeated observations will be fit using maximum likelihood through 'xtmixed' in the

software package Stata to study group-level temporal dynamics in daily measures of the primary and secondary outcomes.

Sample and Effect-size Estimation

We will recruit a total of 150 participants and will assume a 90% retention rate through the 9-month study period. This is a conservative estimate of attrition, as previous research in the same clinic and with a similar population observed only 6% attrition over 12-month study periods [44,48]. Given the study objectives of establishing acceptability, feasibility, and preliminary effectiveness, the targeted sample size may not have the power to detect many of the effects that would be clinically significant. Nonetheless, effect size calculations associated with 80% power (2-tailed test) with regard to the primary outcomes at month nine have been carried out. A recent study conducted at Mildmay suggested that mean ART adherence rates are ~ 75% (SD = 20) as measured by MEMS caps [44]. Using these parameters as estimates of adherence for the control group, and 10% attrition at month nine, a sample size of 150 will provide sufficient power to detect a 9% difference in mean adherence between the pooled intervention groups and the control group (effect size = .47), and a roughly 11% difference in mean adherence between the two intervention groups. This translates to the study being able to detect medium effect sizes.

Qualitative Analysis

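### McNemar's test is named for comparing arms on dichotomous outcomes, but the arms are independent and no pairs exist, so the unadjusted test is wrong as written

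*Combined protocol and SAP*

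**What the plan says.** The protocol's Statistical Methods and Analyses section sets the rule for binary outcomes, naming viral suppression as its example: "a non-parametric McNemar's test and an analogous multiple logistic regression will be used to control for covariates to assess group differences". The declared purpose is therefore a comparison between arms.

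The design is given under Study Design as a "three-armed randomized controlled trial (two intervention groups and one control group) with randomization at the individual level". Randomization and Allocation adds: "The distribution ratios for the randomization will be 1:1:1". Matching, crossover and paired allocation are not described anywhere.

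Two efficacy outcomes are dichotomous, and both are secondary. Retention in care is "measured as an indicator of whether the participants are still active clients at the clinic at the end of the nine-month study". For viral suppression, "The analysis will examine the intervention effects on the likelihood of being virally suppressed at the end of the nine-month study period". Each asks for an arm effect at one time point.

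**The concern.** McNemar's test takes pairs of binary observations and asks whether the discordant pairs split evenly in the two directions. Participants in different arms here are unrelated people, so there are two ways to apply it, and neither does what the plan asks.

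- **Across arms.** The analyst must pair people arbitrarily. The p-value then depends on an ordering that carries no information. The test also takes only two groups of equal size at a time.
- **Within person.** The schedule in Figure 2 marks viral load at allocation and later, so a before-and-after pair could be built for suppression. That tests change over time, which can be large in every arm with no intervention effect. Retention is a single end-of-study indicator with no baseline counterpart, so no such pair exists.

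At stake is the unadjusted result for both secondary efficacy outcomes. It could not be reproduced from the plan, or it would answer a different question. The results are also meant to inform a larger trial, into which the wording could be carried.

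**Working it through.** The documents give no rate, power or sample size for a dichotomous outcome, so there is no figure of theirs to reproduce. All rates below are assumed, and two-sided alpha is taken as 0.05 because the plan does not state it.

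**Number per arm.** Sample and Effect-size Estimation gives 150 recruited and 90% retained: 150/3 × 0.90 = 45 per arm, or 90 in the two intervention arms together.

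**1. Dependence on the pairing.** Suppose 34/45 are suppressed in one arm and 42/45 in the other. If *a* pairs have both members suppressed, the discordant counts are 42 − *a* and 34 − *a*. Under random pairing *a* is hypergeometric and runs from 34 + 42 − 45 = 31 to 34. The p-value is the exact two-sided binomial at one half.

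| *a* | Discordant pairs | Exact McNemar p | Share of random pairings |
|---|---|---|---|
| 31 | 11 vs 3 | 0.0574 | 42.2% |
| 32 | 10 vs 2 | 0.0386 | 43.5% |
| 33 | 9 vs 1 | 0.0215 | 13.2% |
| 34 | 8 vs 0 | 0.0078 | 1.2% |

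So 57.8% of pairings give p < 0.05 and 42.2% do not, from identical data. Fisher's exact test gives 0.039 whatever the order. Two further assumed cases behave the same way:

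- 36/45 vs 43/45: McNemar p from 0.016 to 0.065, with 36% of pairings below 0.05; Fisher 0.0496.
- 32/45 vs 40/45: McNemar p from 0.008 to 0.096; Fisher 0.063.

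**2. Pooled intervention arms against control.** The sample size section bases its adherence calculation on the "difference in mean adherence between the pooled intervention groups and the control group". Applying the same contrast to binary outcomes is an assumption. With 90 against 45, at most 45 pairs can be formed, so 90 − 45 = 45 intervention participants go unused. Exact power:

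| Control / intervention rate | McNemar, 45 pairs | Fisher, 45 vs 90 |
|---|---|---|
| 70% / 90% | 57.3% | 78.0% |
| 75% / 90% | 35.7% | 56.5% |
| 80% / 95% | 45.8% | 72.4% |

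**3. Two equal arms of 45.** At 70% vs 90%, power is 57.3% (McNemar) against 57.5% (Fisher). With no difference, 80% vs 80%, the rejection rate is 2.7% against 2.6%. On average almost nothing is lost; the defect that remains is that the p-value is not unique.

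**4. Within-person version with no arm effect.** Simulated McNemar tests with the same change in every arm, and each person's two results drawn independently:

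| Assumed suppression, before → month nine | Rejects, n = 45 | Rejects, n = 135 |
|---|---|---|
| 30% → 80% | over 99% | over 99% |
| 50% → 80% | 86% | over 99% |
| 70% → 80% | 19% | 47% |
| 80% → 80% | 4.5% | 4.8% |

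The rejection rate follows the size of the change over time and says nothing about the arms.

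**The case against.** The strongest reply is that little depends on this. The same sentence plans a multiple logistic regression, which is a valid comparison between arms. The four primary electronic adherence outcomes and the sample size calculation are untouched, the trial seeks only preliminary efficacy, and between two equal arms the average loss is negligible. Nobody proposes to pair strangers at random, so this may simply be a misnamed test. All of that is fair and limits the severity. It does not make the sentence correct: the analyst must still invent pairs or depart from the plan.

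Four narrower points also stand.

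- The pooled contrast is stated only for mean adherence, so the power loss in step 2 is conditional on its use for binary outcomes.
- Retention comes from clinic records and counts people who stop attending. Its natural denominator is everyone randomised, 150/3 = 50 per arm, so the illustrations at 45 fit viral suppression only.
- A significant within-arm change cannot be taken for granted. It depends on suppression at the baseline used, and participants may have been on treatment for some months by allocation. At 70% → 80% the test rejects in only 19% of simulations with 45 people.
- A replacement worded as chi-square or Fisher would leave a choice of its own. For 34/45 vs 42/45 the two give 0.020 and 0.039; for 32/45 vs 40/45 they give 0.035 and 0.063, on opposite sides of 0.05. One test should be named.

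**Conclusion.** The concern holds: the unadjusted test for dichotomous outcomes is wrong as written, and it should be fixed. This is not a matter of missing detail, because the named test does not fit unmatched arms, and the within-person alternative answers another question for viral suppression and is unavailable for retention.

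The size depends on use. Across two arms, the same assumed data can fall on either side of 0.05. In a pooled contrast, if one is made, half the intervention participants are dropped and power falls by about 21 to 27 percentage points over the assumed rates. In a comparison of two equal arms, average power and type I error barely change. The error is confined to the unadjusted analysis of the two secondary efficacy outcomes. The figures rest on 45 per arm, assumed suppression rates and two-sided alpha of 0.05; the conclusion about the test does not depend on them.

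**What to change.** In Statistical Methods and Analyses, replace McNemar's test with one named test for independent groups, for example Fisher's exact test on the arm-by-outcome table. State which contrasts it applies to for retention and viral suppression; pooled intervention against control and Incentives against Messages would match the contrasts used for sample size. State the denominator for each outcome. Keep the covariate-adjusted logistic regression as the between-arm analysis, and drop the description of it as analogous to McNemar's test, whose regression counterpart is conditional logistic regression. If McNemar's test is retained, limit it to describing within-arm change in viral suppression and say that it is not evidence of an arm effect.

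The cost is a sentence or two of analysis wording and no new data. The protocol reports data collection complete and analysis under way, so the change should be recorded and dated as a correction to the plan.

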The MEMS data will be automatically downloaded and stored electronically using the MEMS cap software that will be installed on a tablet accessible by the study coordinator. The other study data, including participants’ survey responses, monthly visit reports, and other information about study dropout, will be recorded by study personnel in Microsoft Access templates designed by the research team. These electronic data will be safely stored at Mildmay and securely transferred to the research team in the United States periodically during the study period, and at the end of the nine-month study.

Chart Abstraction

Participant’s viral load will be used as a complementary measure to the MEMS data for the assessment of ART adherence. They are now a part of routine clinical care at Mildmay with tests carried out when someone receives a positive HIV test result, after six and 12 months of the initial diagnosis, and every 12 months thereafter. Consequently, the results of the viral load

test will be chart abstracted and the data abstraction will be timed with the routine tests for the participants.

[Participant Tracking](#)

Extensive tracking information will be collected at recruitment and will be verified at each study visit. This will include mobile phone numbers, home address, and email addresses, as well as the contact information for two individuals who live in the same community and who the participant is comfortable and familiar with. These additional contacts are collected to ensure that the participant can be located in case their contact information changes. These procedures have limited attrition in the researchers' previous studies to about 5% [44,48].

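### For retention in care, ordinary logistic regression may give no finite odds ratio, and for a given control rate this risk rises as the intervention arms retain more people

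*Combined protocol and SAP*

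**What the plan says.** Statistical Methods and Analyses assigns dichotomous variables, with viral suppression as the example, to McNemar's test and to a model: "an analogous multiple logistic regression will be used to control for covariates to assess group differences". The only rule for choosing covariates is in the preceding sentence on analysis of covariance: "controlling for the participant characteristics that are found to differentiate the groups at baseline". The number of covariates is open, and neither a penalised or exact method nor a rule for few events is given.

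The Outcomes section has two binary efficacy outcomes. Retention in care indicates whether the participant is still an active client at nine months, taken from clinic records. Viral suppression uses a threshold of 200 copies/mL. No expected rate is given for either.

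The nearest figures are for study attrition:
- Sample and Effect-size Estimation: "We will recruit a total of 150 participants and will assume a 90% retention rate through the 9-month study period".
- The same section: "previous research in the same clinic and with a similar population observed only 6% attrition over 12-month study periods".
- Participant Tracking: tracking procedures held attrition in the team's "previous studies to about 5"%.

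Allocation is described as "using an even allocation ratio of 1:1:1 between the three study groups", so about 50 per arm.

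**The concern.** A maximum-likelihood odds ratio does not exist as a finite number when one arm has no events, or when some combination of arm and covariates splits events from non-events (separation). With only a handful of losses from care per arm this can happen by chance, and each added covariate makes it more likely. For a given control rate, the fewer people an intervention arm loses, the likelier it is to have no events. The planned estimate is therefore most at risk when an arm does well on this outcome.

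The plan offers no substitute. McNemar's test is for paired data and does not compare independent arms, so the logistic model is the only between-arm analysis that its sentence on dichotomous variables supplies. The Dissemination section says the results will feed the design of a larger trial, and that needs a usable estimate with an interval.

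**Working it through.** **Plan's own figure.** None exists for this point. The only computed size figure in the plan concerns mean adherence; no event count or power is stated for a binary outcome.

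**Inputs.** 150 participants, 1:1:1, 50 per arm. All 150 are kept in the denominator because the outcome comes from clinic records. Loss rates p of 10%, 6% and 5% are the attrition figures above, used as a proxy for no longer being an active client. The number of covariates (0 to 5) and their form (binary at 30% prevalence and standard normal, unrelated to outcome) are assumptions.

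**Expected events.** 150 × 0.10 = 15; 150 × 0.06 = 9; 150 × 0.05 = 7.5. Per arm: 5, 3 and 2.5. With two arm terms and one covariate there are 9/3 = 3 to 15/3 = 5 events per non-intercept parameter. With five covariates there are 9/7 = 1.3 to 15/7 = 2.1.

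**Chance that at least one arm has no events, same rate in all arms:** 1 − [1 − (1 − p)^50]^3.
- p = 10%: 0.90^50 = 0.0052, giving 1.5%.
- p = 6%: 0.94^50 = 0.0453, giving 13.0%.
- p = 5%: 0.95^50 = 0.0769, giving 21.4%.

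**Control 10%, both intervention arms 5%:** 1 − (1 − 0.0052)(1 − 0.0769)^2 = 15.2%.

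**Any infinite coefficient, covariates included.** Simulation with no true effect, 1,000 trials per setting, separation detected by linear programming:

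| Loss rate | 0 covariates | 1 | 3 | 5 |
|---|---|---|---|---|
| 10% | 1.6% | 1.8% | 2.8% | 3.6% |
| 6% | 14.2% | 16.8% | 21.5% | 27.6% |
| 5% | 23.2% | 28.2% | 32.9% | 37.9% |

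The Monte Carlo standard error is about 1.4 points at 27.6% (√(0.276 × 0.724/1000)). Repeat simulations gave about 1-5% at 10%, 11-24% at 6%, and 15-26% for 10% control with 5% in both intervention arms. Taking all runs together gives 1-5%, 11-28% and 15-26%.

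**Precision when the estimate is finite.** For one arm against another with no effect, the standard error of the log odds ratio is √[2(1/e + 1/(50 − e))], with e events per arm.
- e = 5: 0.667, so a 95% interval around 1 of 0.27 to 3.69.
- e = 3: 0.842, so 0.19 to 5.21.

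**Does a penalised fit narrow this?** In a small simulation (150 trials per setting, so approximate), the median ratio of upper to lower 95% limit was 16.6 for ordinary logistic regression with five covariates and 14.5 for Firth with one covariate at 10%. At 6% it was 32.7 (converged fits only) against 33.6 (all trials). There is essentially no gain in width.

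**Viral suppression, for contrast.** With 135 analysed (45 per arm) and assumed failure rates of 5%, 10%, 20%, 30% and 40%, events are about 7, 14, 27, 41 and 54. The chance of an arm with none is 27%, 2.6%, 0.01%, and then about zero.

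**The case against.** Several counter-arguments have force.

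- **The outcome the plan names.** Its example is viral suppression, and no rate for that is given. A reader might infer that every binary outcome here is sparse. The documents do not support this: at 20% failure or more the problem all but disappears. This stands, and it limits the point to retention in care.
- **The proxy.** Attrition from the study is not the same as leaving the clinic. Secondary Outcome 1 counts people as lost after six months or more without a visit. If that rule defines inactive status, someone lost by month nine must have stopped attending by about month three, so events could be fewer. The same section calls failure to stay in care common among treatment initiators, so events could also be more numerous. This stands as a stated assumption.
- **Frequency.** A reader might infer that odds ratios will often be infinite. At the 10% loss the plan assumes, equal in all arms, it happens in only about 1-5% of trials. It becomes material at the 6% and 5% the plan also cites, or when the intervention arms do better than control.
- **Covariates.** Five is our assumption; after randomisation few or none may differ. But with no covariates at all the risk is still about 13% at 6%.
- **Disclosed low power.** Sample and Effect-size Estimation and Limitations both admit the small sample, and wide intervals follow from that. This answers the imprecision, but not an estimator that can return no finite value.
- **Wald inference is not specified.** Likelihood-ratio tests could be used with the ordinary model. Simulated Wald tests rejected a true null in about 1.4-3.4% of trials against a nominal 5%, so false positives are not inflated. The infinite odds ratio remains whichever test is used.

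**Conclusion.** The point holds for retention in care, as a moderate one about a secondary outcome in a pilot. If loss from care is close to the cited attrition, about 8 to 15 events are expected. The planned model then has an infinite coefficient in about 1-5% of trials at 10%, 11-28% at 6%, and 15-26% if both intervention arms halve a 10% rate. For a given control rate, the risk of failure rises as the intervention arms improve. This rests on attrition as a stand-in for active-client status, 50 per arm, and 0 to 5 covariates unrelated to outcome.

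It does not show that viral suppression has the same problem, or that changing the estimator would make the odds ratios precise.

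**What to change.** In Statistical Methods and Analyses, for retention in care:

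1. Replace the ordinary multiple logistic regression with Firth-penalised logistic regression and profile penalised-likelihood intervals. Include arm and one pre-specified covariate already collected, namely baseline MEMS adherence from the month before the intervention.
2. Report beside it the unadjusted risk differences between arms with Newcombe intervals.
3. Apply the same method to viral suppression only if its events prove similarly sparse. A simple trigger would be 15 or fewer unsuppressed participants in all arms together, counted before arm labels are opened.

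As an illustration, suppose 5 of 50 are lost in control and 0 of 50 in an intervention arm. The ordinary fit has no finite log odds ratio. Firth without covariates adds a half to each cell: (0.5 × 45.5)/(50.5 × 5.5) = 0.08. The Wilson limits are 4.3% to 21.4% for 5/50 and 0% to 7.1% for 0/50. The Newcombe interval for the 10-point difference therefore runs from 10 − √(5.65² + 7.14²) = 0.9 to 10 + √(11.36² + 0²) = 21.4 points.

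The cost is a few lines of text and standard software, slight shrinkage of the odds ratios, and fewer covariates. Intervals will be no narrower. The document says that data collection is complete, analyses are ongoing and the impact analyst is to be blinded, so the change should be dated and recorded before arm labels are opened.
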